10.2.2.4 Efficacy Analyses

10.2.2.4.1 Primary Efficacy Analysis

The primary efficacy analysis will be the evaluation of OS and PFS based on the ITT Population.

Overall survival is defined as the time interval from randomization to death of any cause. Patients who are alive will be censored at the last known date alive or data analysis cutoff date, whichever is earlier. PFS is defined as the time interval from randomization to tumor progression or death. Accordingly, the precise definition of progression and the timing of imaging scans to progression are very important. Every effort must be made to assure that timeframes for follow-up imaging scans are achieved, so that both treatment groups can be usefully compared. Assessments must be adequate to evaluate target lesions, non-target lesions, and to search for new lesions.

PFS will be based on RECIST 1.1 response guidelines modified to use irRC-specific confirmation. PFS will be defined as the time from randomization to disease progression or death (any cause), whichever occurs first. The irRC modification requires a confirmation of progressive disease (PD) at least 4 weeks later with imaging; once confirmed, the date of progression is defined as the first date that the total tumor burden was shown to have increased by at least 20% compared with the nadir. Patients who do not have disease progression or have not died will be censored at the date when the last tumor assessment determines a lack of progression. If a patient begins a new anti-cancer therapy or has radiotherapy or surgery at a lesion site prior to confirmed progression (or death), the patient will be censored at the last assessment where the patient was documented as progression free prior to the intervention. Patients with two or more missing response assessments prior to a visit with progression (or death) will be censored at the last visit where the patient is documented to be progression free.

The primary efficacy analysis will be the evaluation of OS and PFS using Kaplan-Meier methodology and will be performed on the ITT Population for each treatment arm. Kaplan-Meier plots and 95% confidence intervals (CIs) for 75%, 50% and 25% survival, if reached, will be provided for each treatment group.

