Appendix D Comparison of RECIST v1.1 vs. RECIST-based irRC

	RECIST v1.1	RECIST-based irRC
New, Measurable lesions (≥ 10 mm)	Recorded as PD	Incorporated into tumor burden (see Appendix C)
New, non-measurable lesions (< 10 mm)	Recorded as PD	Do not define progression (but preclude irCR)
Non-Target Lesions	Contributes to best overall response (CR, PR, SD, PD)	Contribute to irCR (complete disappearance required)
CR	Disappearance of all lesion in 2 consecutive observations ≥ 4 weeks apart	Disappearance of all lesions in 2 consecutive observations ≥ 4 weeks apart
PR	$\geq 30\%$ decrease in sum of the longest diameter of all index lesions compared with baseline in 2 observations ≥ 4 weeks apart, in the absence of new lesions or unequivocal progression of non-index lesions	$\geq 30\%$ decrease in tumor burden compared with baseline in 2 observations ≥ 4 weeks apart
SD	Neither sufficient shrinkage to qualify for PR or increase to qualify for PD when compared to the smallest sum of diameters while on study	30% decrease in tumor burden compared with baseline cannot be established nor 20% increase when compared with nadir
PD	$\geq 20\%$ increase in the sum of the diameters of the target lesions when compared to the smallest sum while on study. The sum must also demonstrate an absolute increase of ≥ 5 mm. The appearance of ≥ 1 new lesion is considered PD	$\geq 20\%$ increase in tumor burden compared with nadir (at any single timepoint) in 2 consecutive measurements ≥ 4 weeks apart.

CR = complete response; irRC = immune-related response criteria; irCR = immune-related complete response; PD = progressive disease; PR = partial response; RECIST = response evaluation criteria in solid tumors; SD = stable disease.

Overall Response Using the irRC

The overall response according to the irRC is derived from timepoint response assessments (based on tumor burden) as follows:

- Immune-related complete response (irCR): complete disappearance of all lesions (whether measurable or not, and no new lesions) and confirmation by a repeat, consecutive assessment no less than 4 weeks from the date first documented
- Immune-related partial response (irPR): decrease in tumor burden $\geq 30\%$ relative to baseline and confirmed by a consecutive assessment at least 4 weeks after first documentation
- Immune-related Stable Disease (irSD): not meeting criteria for irCR or irPR, in absence of irPD

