# **5 STUDY ENDPOINTS**

# 5.1 Efficacy Endpoints

# 5.1.1 Primary Efficacy Endpoint

# 5.1.1.1 **Progression free Survival (PFS)**

PFS will be based on RECIST 1.1 response guidelines modified to use irRC-specific confirmation. Progression-free survival (PFS) in months is calculated as: (date of first progression or death (any reason) – date of randomization +1)/30.4375. The irRC modification requires a confirmation of progressive disease (PD) at least 4 weeks later with imaging; once confirmed, the date of progression is defined as the first date the total tumor burden was shown to have increased by at least 20% compared with nadir. Patients without progression or death are censored at the date of the last disease assessment. If a patient begins a new anti-cancer therapy or has radiotherapy or surgery at a lesion site prior to confirmed progression (or death), the patient will be censored at the last assessment where the patient was documented as progression free prior to the intervention. Patients with two or more missing response assessments prior to a visit with progression (or death) will be censored at the last visit where the patient is documented to be progression free. Patients without disease assessment post-baseline will be censored at the randomization date. As needed, we will use Table 3 to specify how dates of progression events and dates for censoring of progression data are assigned. Table 3 represents an analysis that only includes well-documented and verifiable progression events. In Table 3, the progression dates are:

- Based only on radiological assessments verified by an IRC and symptomatic deterioration date assessed by study investigator.
- Assigned to the first time when tumor progression was noted.
- The date of death when the patient is closely followed. However, deaths occurring after two or more missed tumor assessments (> 91 days after last tumor assessment) are censored at the last visit.

Progressive disease will be assessed by the unidimensional measurements approach of the Immune-related Response Criteria.

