# 5.1.2 Secondary Efficacy Endpoint

# 5.1.2.1 PFR at 6 Months

PFR at 6 months will be calculated using Kaplan-Meier method.

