# 7.6.2 Analysis of Secondary Efficacy Variables

# 7.6.2.1 PFR at 6 Months

PFR at 6 months using Kaplan-Meier method, with 95% and 80% confidence intervals (CIs) by treatment arm will be presented. If the Lower Confidence Limit of the 80% CI is greater than the assumed unaccepted PFR rate of 25%, it would serve as a signal that PFR at 6 months is higher than 25%.

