# 8 CHANGES FROM THE PROTOCOL SPECIFIED STATISTICAL ANALYSES

If discrepancies exist between the text of the statistical analysis as planned in the protocol, and the final SAP, a protocol amendment will not be issued, and the SAP will prevail.

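### The SAP censors event-free patients at their last scan whatever it showed, so a final unconfirmed irPD scan counts as progression-free time that the protocol would not credit

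*SAP*

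**What the plan says.** Both documents count progression only once it is confirmed. SAP 5.1.1.1 puts it this way: "The irRC modification requires a confirmation of progressive disease (PD) at least 4 weeks later with imaging". A single irPD scan with nothing after it is therefore not an event.

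The documents differ on where such a patient is censored.

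- Protocol 10.2.2.4.1: a patient with neither progression nor death "will be censored at the date when the last tumor assessment determines a lack of progression".
- SAP 5.1.1.1: "Patients without progression or death are censored at the date of the last disease assessment". The last row of SAP Table 3 (no progression or death) likewise assigns the last tumor assessment date.

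Elsewhere in the same section the SAP keeps the qualifier. For new therapy, "the patient will be censored at the last assessment where the patient was documented as progression free prior to the intervention"; the sentence on two or more missed assessments is worded to the same effect.

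SAP section 8 says that where the two documents differ, "a protocol amendment will not be issued, and the SAP will prevail". It does not list this change.

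The date feeds the 6-month PFR, because "PFR at 6 months will be calculated using Kaplan-Meier method" (SAP 5.1.2.1). It also feeds the signal rule in SAP 7.6.2.1, which begins "If the Lower Confidence Limit of the 80% CI is greater than the assumed unaccepted PFR rate of 25" (per cent).

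**The concern.** Consider a patient whose last scan shows tumor burden at least 20% above nadir. No confirming scan follows, and there is no new therapy, symptomatic deterioration or death close enough to count. Under the protocol this scan cannot serve as the censoring date, since it does not show an absence of progression. Under the SAP it does serve, so the patient is treated as progression free through a scan that showed growth. Patients who miss the confirming scan may well have a worse prognosis, so the censoring is unlikely to be neutral.

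At stake are one of the two primary endpoints, the 6-month PFR and its 80% lower-limit signal. There is also a derivation problem. Within the SAP, the text on progression or death after missed assessments censors at the last progression-free visit, while the matching Table 3 row gives the last tumor assessment. A programmer cannot obtain one date from both.

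**Working it through.** **1. The design reproduces.** Exponential medians of 3 and 5.2 months give 6-month PFRs of 0.5^(6/3) = 25.0% and 0.5^(6/5.2) = 44.9%, matching the stated 25% and 45%. The two-stage rule (at least 6 of 18, then at least 14 of 40) has exact type I error 0.080 and power 0.856, against the stated alpha 0.1 and beta 0.15. The point does not touch these boundaries.

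**2. Is the irPD scan one that shows no progression?** Protocol Appendix D defines irRC stable disease by "30% decrease in tumor burden compared with baseline cannot be established nor 20% increase when compared with nadir". A scan 20% or more above nadir is outside that definition, so the natural protocol date is the scan before it (baseline, if it was the first on-study scan).

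**3. Direction.** Moving a censoring date later, with events unchanged, can only enlarge risk sets. No Kaplan-Meier factor can fall, so the SAP curve is never below the protocol curve.

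**4. Size.** Inputs and assumptions:

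- Scans every 6 weeks in year 1 (both documents), so four fall before 6 months: weeks 6, 12, 18 and 24.
- h is the chance of a first irPD at each scan, set so that the PFR equals a reference value S when every first irPD counts as an event: h = 1 − S^(1/4). For S = 25%, h = 0.2929; for S = 45%, h = 0.1810.
- q is the share of first irPDs that are the last scan, with none of the other outcomes above. **The documents give no value; 5% to 20% is an assumed range.**

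Kaplan-Meier hazard per scan:

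- SAP: the unconfirmed patients stay in the risk set at the irPD scan, giving (1−q)h.
- Protocol: they leave one scan earlier, giving (1−q)h/(1−qh).

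The 6-month PFR is (1 − hazard)^4. Example, S = 25% and q = 10%: the SAP hazard is 0.9 × 0.2929 = 0.2636 and the PFR is 0.7364^4 = 29.4%. The protocol hazard is 0.2636/0.9707 = 0.2716 and the PFR is 0.7284^4 = 28.2%.

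| Reference S | q | Protocol | SAP | Gap (points) |
|---|---|---|---|---|
| 25% | 5% | 26.5% | 27.1% | 0.6 |
| 25% | 10% | 28.2% | 29.4% | 1.2 |
| 25% | 20% | 31.8% | 34.4% | 2.5 |
| 45% | 5% | 46.7% | 47.0% | 0.4 |
| 45% | 10% | 48.4% | 49.1% | 0.7 |
| 45% | 20% | 52.2% | 53.5% | 1.4 |

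Gaps are taken before rounding.

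**5. Signal rule.** Simulation with 40 patients, 6,000 runs per scenario, log-log 80% interval and reference 25%. The chance that the lower limit exceeds 25% is about 0.10 when every first irPD is an event. At q = 10% it is 0.19 (protocol) and 0.24 (SAP); at q = 20%, 0.32 and 0.45. A linear interval gives 0.18 and 0.23, then 0.31 and 0.43. The SAP estimate was below the protocol estimate in no run.

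**6. Median.** With S = 25% and q = 10%, the curve after scans 2 and 3 is 0.531 and 0.387 (protocol) or 0.542 and 0.399 (SAP). Both cross 50% at week 18, so the median is the same.

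**The case against.** **The affected group is narrow.** SAP Table 3 already counts as events symptomatic deterioration, and death, before the first PD assessment or between adequate visits. New therapy has its own rule. A confirmatory scan is scheduled (footnote g of the schedules of events), and patients who meet RECIST progression but are clinically well may stay on treatment (Protocol 6.3), so they would normally be re-scanned. This stands, and it argues against a large q. It does not bring q to zero. Footnote b ends staging at progression, and the instruction to keep scanning after stopping treatment covers only patients who stop for other reasons.

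**The analysis is descriptive.** Primary results are Kaplan-Meier summaries by arm, p-values are nominal, futility is non-binding, the 80% limit is only a signal on a secondary endpoint, and the same rule applies to both arms. This also stands and limits severity.

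**An unconfirmed irPD is arguably not progression under the protocol either.** A strict reader could then call the two rules equivalent. The protocol's qualifier and the Appendix D definition of stable disease make that reading strained.

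**Stronger readings are tempting but not supported.** A reader might charge the SAP wording with the whole rise from 25% to 34.4% at q = 20%. Of those 9.4 points, 6.8 (31.8 − 25) arise under the protocol rule too, from the confirmation requirement that both documents share. A reader might also start from a 3-month median read on the scan grid, giving 0.5^(5.52/3) = 28% at week 24. The 3 points above 25% come from scan timing, not censoring. Finally, a reader might conclude that an unconfirmed irPD should be a primary event. Both documents define progression as confirmed irPD, and such a rule would turn patients merely awaiting confirmation at a data cutoff into events.

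**Conclusion.** The discrepancy holds. The governing SAP text and the last row of Table 3 drop a protocol qualifier that the SAP keeps in its own new-therapy and missed-assessment sentences. The direction is certain: the SAP rule cannot lower the Kaplan-Meier 6-month PFR relative to the protocol rule, and raises it when such patients occur. The PFR effect is small to modest, about 0.6 to 2.5 points at a reference of 25% and 0.4 to 1.4 points at 45%, for q between 5% and 20%. The effect on the signal is more visible: at the unacceptable rate, 0.05 (0.24 − 0.19) is added to the chance of a false signal at q = 10% and 0.13 (0.45 − 0.32) at q = 20%.

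These sizes rest on an assumed q, a constant hazard per scan and exact 6-weekly scanning. It does not follow that PFS medians must rise. Severity is moderate: worth correcting before database lock, but not a flaw that invalidates the design.

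**What to change.** - In SAP 5.1.1.1, censor patients without an event at the last assessment documented as progression free. Make the same change in every Table 3 row that assigns the last tumor assessment date, so that text, table and protocol agree. Duration of response and duration of clinical benefit inherit the PFS censoring rule and follow automatically.
- Keep confirmed irPD as the primary progression event.
- Pre-specify one sensitivity analysis that counts a final unconfirmed irPD with no later scan as progression on that scan date, excluding patients still within the confirmation window at data cutoff. The documents give only a minimum of 4 weeks for confirmation, so the SAP should state the window's upper end for this analysis.
- Report by arm how many patients end on an unconfirmed irPD, so that q becomes known.

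The cost is SAP wording and one derivation rule, with no added patients, scans or procedures. Reported PFS and PFR may be slightly less favourable.

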#### IMDZ-C232

Peripheral blood will be collected for immunogenicity assays at baseline, then on Days 42, 70, and 98 ( $\pm$  2weeks). Tissue biopsies will be taken in each treatment group from consenting subjects before treatment and on Day 42, on Day 98 ( $\pm$  2 weeks), at 6 months or longer (for patients with treatment response), and at the time of progression to assess immune cell invasion, including changes in PD-L1, CD4, CD8/Ki-67 and/or CD3/perforin expression. If a patient undergoes a tumor biopsy at any time after disease progression, investigators are strongly encouraged to provide biopsy tissue to the sponsor for immune response and tumor changes analysis.

Imaging will be performed approximately every 6 weeks for 12 months, then every 12 weeks for tumor staging until progression. Tumor responses will be assessed at the sites by evaluating tumor images/scans using RECIST (v1.1) modified to use irRC-specified confirmation and unidimensional tumor measurements. Adjudication will be performed by blinded independent central review (BICR) following the same rules. The irRC modification requires a confirmation of CR/PR/progressive disease (PD) at least 4 weeks later with imaging; once confirmed, the date of progression is defined as the first date that the total tumor burden was shown to have increased by at least 20% compared with the nadir.

Patients will be followed until confirmed radiographic disease progression to determine ORR and PFS. In addition, OS status will be followed up until the end of the trial. If a patient dies, the date of death will be documented by the local physician and/or registries.

All SAEs, DLTs, and medical events of interest (MEOIs) deemed potentially related to the study agents will be reviewed by the Sponsor and an independent Data Monitoring Committee (DMC).

Following completion of CMB305 dosing, patients will continue with clinical assessment and imaging approximately every 6 weeks until disease progression, as defined by RECIST (v1.1) modified to use irRC. The expected duration of a patient's participation in the trial is up to 2.1 years, including Screening, Treatment Phase, Booster Phase (for patients in the combined treatment arm), and Maintenance Phase (with follow-up visits until disease progression). Patients will then enter the Survival Follow-up Phase and their physicians will be contacted every 3 months by telephone to assess OS.

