#### IMDZ-C232

Abbreviations: AE = adverse event, CT = computed tomography; ECG = electrocardiogram; ECOG = Eastern Cooperative Oncology Group; HepB = hepatitis B; HepC = hepatitis C; HIPAA = Human insurance Portability and Accountability Act; HIV = Human immunodeficiency Virus; meds = medications; mos = months; PBMC = peripheral blood mononuclear cells; SAE = serious adverse event.

- a. A window of ±3 days is permitted for Visits 3 through 12. Follow-up phase visits (Visits 13+) will be permitted a window of ±4 days, Tumor assessments will be permitted a window of ±1 week.
- b. Patients will be followed with visits every 3 weeks (±4 days) for 2 years (from Day 0) for until progression. Tumor size will be assessed every 6 weeks for the first year, then every 12 weeks until progression. Patients will then have no further staging procedures. Tumor biopsies will be obtained at 6 months or longer for patients with treatment response. Tumor biopsies will also be obtained at time of progression.
- c. Informed consent and HIPAA authorization must be signed before any screening study-related procedures are initiated. Three informed consents will be used: one to screen tumor sample for NY-ESO-1, one to engage in the study protocol, and an agreement to continue in the study and obtain peripheral blood samples and biopsies if the patient meets the criteria for progressive disease but wishes to remain on study.
- d. Documentation of NY-ESO-1 expression in prior tumor samples may have been collected from any procedure performed before baseline activities. There is no time limit for use of the results from the IMDZ-approved central lab.
- e. Vital sign measurements include temperature, pulse, respiratory rate, and resting systolic and diastolic blood pressure. On the day of each dosing, vital signs will be obtained pre-dosing and 30 minutes after dosing. For the first atezolizumab infusion, the patient's vital signs (HR, respiratory rate, BP, and temperature) should be measured within 15 minutes of the infusion, during the 60-minute infusion (every 15 [± 5] minutes), and 30 minutes after the infusion. For subsequent infusions, vital signs do not need to be obtained during the infusion if the prior infusion was tolerated without symptoms.
- f. Once the baseline physical exam has been conducted, a simple symptom-directed physical exam should be performed for all subsequent visits. Height and weight will be collected at Day 0 only.

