# **4 SAMPLE SIZE DETERMINATION**

Sample size was calculated using a Simon 2-stage design, assuming an unacceptable progression-free survival rate (PFR) of 25% and an acceptable PFR of 45% at 6 months, corresponding to an unacceptable and desirable median PFS of 3 months and 5.2 months, respectively and an exponential survival distribution, 40 patients in each arm (alpha=0.1, beta=0.15) were required. For this study, two groups of up to 40 patients each (up to 80 patients) were to be dosed with CMB305 with atezolizumab or with atezolizumab alone to assess PFS at 6 months and median of PFS with 95% CIs. If favorable results are observed, the study may be expanded to improve the estimates of PFS.

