Death before first PD assessmentDate of deathProgressedDeath between adequate assessment visitsDate of deathProgressedDeath or progression after two or more missed visitDate of last tumor assessmentCensoredNew anti-cancer therapy or radiotherapy or surgery at a lesion siteDate of last tumor assessment where the patient was documented as progression free prior to the interventionCensored	more missed visit		
Death between adequate assessment visitsDate of deathProgressedDeath or progression after two or more missed visitDate of last tumor assessmentCensoredNew anti-cancer therapy or radiotherapy or surgery at a lesion siteDate of last tumor assessment where the patient was documented as progression free prior to the interventionCensored	Death before first PD assessment	Date of death	Progressed
visits       Death or progression after two or more missed visit       Date of last tumor assessment       Censored         New anti-cancer therapy or radiotherapy or surgery at a lesion site       Date of last tumor assessment where the patient was documented as progression free prior to the intervention       Censored	Death between adequate assessment	Date of death	Progressed
Death or progression after two or more missed visitDate of last tumor assessmentCensoredNew anti-cancer therapy or radiotherapy or surgery at a lesion siteDate of last tumor assessment where the patient was documented as progression free prior to the interventionCensored	visits		
missed visit     Date of last tumor assessment where the patient was     Censored       New anti-cancer therapy or radiotherapy or surgery at a lesion site     Date of last tumor assessment where the patient was     Censored	Death or progression after two or more	Date of last tumor assessment	Censored
New anti-cancer therapy or radiotherapy or surgery at a lesion siteDate of last tumor assessment where the patient was documented as progression free prior to the interventionCensored	missed visit		
radiotherapy or surgery at a lesion site   documented as progression free prior to the intervention	New anti-cancer therapy or	Date of last tumor assessment where the patient was	Censored
	radiotherapy or surgery at a lesion site	documented as progression free prior to the intervention	
prior to confirmed progression (or	prior to confirmed progression (or		
death)	death)		
No progression or Death         Date of last tumor assessment         Censored	No progression or Death	Date of last tumor assessment	Censored

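### The PFS rule on two missed assessments does not require them to be consecutive and just before the event, so as written it censors well-dated later progressions

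*SAP*

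**What the plan says.** SAP 5.1.1.1 sets the rule: "Patients with two or more missing response assessments prior to a visit with progression (or death) will be censored". The censoring date follows in the same sentence; the patient is "censored at the last visit where the patient is documented to be progression free". Protocol 10.2.2.4.1 carries the same rule, also with no requirement that the misses be consecutive or adjacent to the event.

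SAP Table 3 has a matching row, "Death or progression after two or more missed visit", which censors at the last tumor assessment. One bullet introducing the table gives a time limit, but for deaths only: "deaths occurring after two or more missed tumor assessments (> 91 days after last tumor assessment) are censored at the last visit". The table's own status is conditional: "As needed, we will use Table 3 to specify how dates of progression events and dates for censoring of progression data are assigned".

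On scan timing, SAP 3.1 says "Imaging will be performed approximately every 6 weeks for 12 months, then every 12 weeks for tumor staging until progression", and footnote a to the SAP schedule of events adds "Tumor assessments will be permitted a window of ±1 week". SAP 4 sizes the trial on an "unacceptable and desirable median PFS of 3 months and 5.2 months". SAP 8 makes the SAP prevail where it differs from the protocol's statistical text.

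**The concern.** A missed-assessment rule exists because a progression found after a long unobserved gap cannot be dated. That reason applies to scans missed just before the event. It does not apply to scans missed earlier and followed by an attended, progression-free scan.

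Take a patient who misses Weeks 6 and 24, is scanned at Weeks 12, 18, 30, 36 and 42, and progresses at Week 48. The progression is dated to within 6 weeks. Under the sentence as written the patient has two missing assessments before the progression visit and is censored at Week 42, just ahead of an observed event. That works against the stated purpose of Table 3, which is to keep well-documented progressions.

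The number of scans that could have been missed grows with time on study, so the events lost belong mainly to patients with long PFS. The affected outputs are the late part of the PFS curve, the 12-month PFS estimate, the exploratory hazard ratio and duration of response, which takes over the PFS censoring rule (SAP 5.1.3.2). Two programmers could also derive different primary-endpoint data from the same text.

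**Working it through.** **1. The plan's own figure.** Two 6-week intervals plus the 1-week window give 2 × 42 + 7 = 91 days. This reproduces the limit in the bullet on deaths exactly. For deaths, then, the SAP treats two missed assessments as one unbroken gap back to the last scan.

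**2. Earliest progression affected.** If only two scans precede the progression scan and both are missed (Weeks 6 and 12, progression at Week 18), the misses are consecutive and both rules censor. The rules first differ when three scans precede it, for example missed-attended-missed or missed-missed-attended at Weeks 6, 12 and 18, with progression at Week 24. That is Day 168, and 168/30.4375 = 5.5 months (5.3 months at Day 161, the early edge of the window). Both exceed the design medians of 3 and 5.2 months.

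**3. Hand check at Week 48.** Take a patient whose disease progresses between Weeks 42 and 48 and who is scanned at Week 48. Seven scans precede it. With independent miss probability m:

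- rule as written: P(at least 2 of 7 missed) = 1 − (1−m)^7 − 7m(1−m)^6
- consecutive rule: P(Weeks 36 and 42 both missed) = m²

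At m = 0.10: 1 − 0.478 − 0.372 = 15.0%, against 1.0%. At m = 0.05: 4.4% against 0.25%. At m = 0.15: 28.3% against 2.25%.

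**4. Whole curve.** Simulation of 100,000 patients per setting. PFS is exponential, as SAP 4 assumes, with the 5.2-month desirable median. Scans are every 42 days to Day 336, then every 84 days. Progression is detected at the first attended scan after it occurs. Deaths and other censoring are ignored. The miss rate is an assumption, shown over a range.

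| Miss rate | Progressions censored, as written | Consecutive rule | Difference per 40 progressions | 12-month KM PFS, as written vs consecutive | Rise in 6-month PFR |
|---|---|---|---|---|---|
| 5% | 3.6% | 0.6% | 1.2 | 23.8% vs 23.3% | 0.04 points |
| 10% | 11.5% | 2.4% | 3.7 | 25.9% vs 24.1% | 0.1 points |
| 15% | 20.6% | 5.2% | 6.2 | 28.1% vs 24.7% | 0.3 points |

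At a 20% miss rate the rise in the 6-month PFR reaches 0.5 points. At the 3-month median the rule as written censors about 1.9%, 6.5% and 12.2% of progressions at 5%, 10% and 15% missed, against 0.6%, 2.2% and 4.6%.

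**5. Where the lost events lie.** At a 5.2-month median and 10% missed, scattered misses alone censor 0.5% of progressions found by 6 months, 18% of those found later than 6 months, and 27% of those found after 12 months.

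**6. Summary times.** Over the miss rates in the table, estimated median PFS is the same under the two rules at both design medians. The time at which 25% remain progression free, which Protocol 10.2.2.4.1 lists, moves one scan step, from Day 336 to Day 420, at a 5.2-month median with 10-15% missed. It does not move at 5% missed or at a 3-month median.

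**The case against.** The strongest reply is that the context points to a gap-based rule. The 91-day limit is exactly two scan intervals plus the window. Table 3 puts death and progression in one row, so one phrase should not carry two meanings there. The table contrasts events between adequate assessments with events after missed ones, which concerns the interval just before the event. SAP 5.1.2.4, 5.1.3.4 and 6.3 also use two missed assessments as a window. This stands as evidence of intent. It does not change the operative sentence, which has no limiter for progressions, and Table 3 applies only as needed.

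It is also fair that the size rests on an assumed miss rate, and that the main PFS summary and the only endpoint used for sizing barely move. With 40 patients, the standard error of a 12-month PFS near 24% is √(0.24 × 0.76/40) = 6.8 points, larger than any shift in the table.

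A reader might infer a difference between arms, because Table 3 says visit and the combination arm has more visits. The documents do not support this. The rule sentence and the bullet both speak of assessments, scan timing is identical in the two arms, and the visit schedules differ only by three early combination-arm visits (Days 14, 28 and 56).

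**Conclusion.** The concern holds for progression events. As written, the rule discards progressions that are dated to within about one or two scan intervals, almost all of them from Week 24 onward. With 5-15% of scans missed independently and a 5.2-month median, about 4-21% of progressions are censored instead of 0.6-5%, and 12-month PFS is raised by about 0.5-3.5 points. These figures assume exponential PFS and no deaths or other dropout.

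A reader might go further and conclude that the primary PFS result or the two-stage futility decision is compromised. The documents do not support that. The median is unchanged between the two rules, the 6-month PFR moves by no more than about 0.5 points, OS is untouched, and SAP 7.6.1.1 and 7.9 label the between-arm comparisons exploratory. Nor is it certain that events would be lost, since a programmer could follow the gap-based intent. What is established is a rule whose plain wording gives a wrong result and which should be corrected before database lock.

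**What to change.** In SAP 5.1.1.1 and Table 3, censor only when *two or more consecutive scheduled tumor assessments immediately before the progression or death were missed*. In Table 3, replace missed visit by *missed scheduled tumor assessments* for consistency.

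Restate the 91-day bullet at the same time, and do not simply extend it to progressions. Once scans are 12-weekly, 84 + 7 = 91 days corresponds to one missed scan. By the SAP's own construction, two missed scans on that schedule would be 2 × 84 + 7 = 175 days, and 42 + 84 + 7 = 133 days for a gap with one missed scan on each schedule. Defining the gap by scheduled assessments avoids the problem.

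Optionally, add a sensitivity analysis that counts every progression as an event whatever was missed before it.

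The cost is SAP wording and the matching derivation, with no new data. Because SAP 8 lets the SAP prevail, aligning Protocol 10.2.2.4.1 is optional.
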